6.4.1 Adverse events and mortality

The incidence of AEs (includes incidence of TEAEs and incidence of post-treatment AEs) will be summarized using MedDRA (version 21.1) preferred terms grouped by primary system organ class. The version number of MedDRA relevant for study evaluation will be stored in the study database.

The incidence of treatment-emergent AEs (TEAEs) occurring during the LTE phase will be tabulated by treatment groups defined for LTE phase. More specifically, AEs are considered to be treatment-emergent if they have started or worsened after first application of study drug up to 2 days after end of treatment with study drug.

An overall summary of the number and percentage of patients with TEAEs will be presented by treatment groups for events from Week 52 to the end of the study. This summary will include the number and the percentage of patients with drug-related TEAEs, treatment emergent serious adverse events (TESAEs), drug-related TESAEs, maximum intensity, AEs leading to permanent discontinuation and AEs with outcome of death.

Incidences of subjects with TEAEs occurring during LTE phase will be summarized by treatment arm and MedDRA terms using frequency tables for the following AE types:

- TEAEs
- Drug-related TEAEs
- TESAEs
- Drug-related TESAEs
- TEAEs of special interests
- Drug-related TEAEs of special interest

Tables for maximum intensity of TEAEs, TESAEs and drug-related TEAEs will be provided.

TEAEs which occurred during the main phase and were ongoing (i.e. not reported as “recovered/resolved” or “recovered/resolved with sequelae”) at the entry in LTE phase will be summarized.

Incidences of TEAEs and TESAEs per 100 person-years will be tabulated. The rate per 100 person-years is calculated as

$$\text{Rate per 100 person-years} = \text{number of events} / (\text{total drug exposure in years} / 100),$$

where 365.25 days are taken as one year.

The incidence of all post-treatment AEs (i.e., AEs occurring more than 2 days after end of treatment with study drug) will be tabulated separately.

AEs with outcome of death will be tabulated from Week 52 to the end of the study.

SAEs, deaths, AE leading to discontinuation and AEs of special interest (as defined in the [protocol Section 7.5.1.6](#)) will be listed. The date, relative day (to study medication) will be included.

Further summaries of AEs by intensity and outcome, may be provided, consistent with Bayer Global Medical Standards.

Incidences of AEs of special interest will be tabulated. The [protocol Section 7.5.1.6](#) specifies symptomatic hypotension and serious hemoptysis as AEs of special interest.

6.4.2 Laboratory data

The safety evaluation of laboratory data will include:

- Incidence rates of treatment-emergent laboratory values outside of normal range.
- Incidence rates of pre-specified laboratory data abnormalities.
- Descriptive analysis of continuous laboratory parameters, and their changes from baseline (i.e. Week 52) by visit.
- Categorical analysis of transitions from low, normal, high from baseline (i.e. Week 52) to post baseline.

6.4.3 Other safety parameters

Descriptive analysis of weight and vital signs, pulse oximetry and their changes from Week 52 (which is the baseline for the LTE analysis) until end of the study will be performed.

Number of subjects with low/normal/high vital signs, will be tabulated by treatment group and

visit. Assessments for orthostatic test will be listed. The number of subjects with abnormal ECG findings, as well as the number of subjects with treatment-emergent ECG abnormalities will be tabulated by treatment group from Week 52 to the end of the study.

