7.6.5 Blood pressure and heart rate measurement - amended

Blood pressure and heart rate will be measured at all visits with the patient in a sitting position, after the patient has been at rest for 5 minutes. The same arm is always used for these measurements.

At certain visits where a blood sample for PK is scheduled after the morning dose of study medication, an additional vital signs measurement (blood pressure and heart rate) will be taken within 20 minutes prior to PK sampling. Please refer to Section 7.1.1.

Methodology: Noninvasive measurement preferably with a validated electronic device in accordance with published guidelines (eg, American Heart Association Recommendations for Blood Pressure Measurement in Humans and Experimental Animals [25]).

Assessment of orthostatic changes¹¹⁶

To assess orthostatic changes, blood pressure and heart rate will be measured with the patient in a supine position, after the patient has rested for 5 minutes. Immediately thereafter, the patient should sit up and blood pressure and heart rate will be measured after the patient has rested for 2 minutes.

These measurements should be performed approximately 2 hours after study medication intake.

Frequency: Visit 11 (Week 39), Visit 12 (Week 52), during the Dose-Titration Period of the Long-Term Extension Phase (Visits 13 to 17).

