7.6.18 Oxygen saturation measurement using forehead pulse oximetry¹¹⁹

Oxygen saturation measurements will be performed in all subjects using non-invasive forehead pulse oximetry expressing the SpO₂ (peripheral oxygen saturation) percentage. At visits with blood pressure measurements to assess orthostatic changes, oxygen saturation will be measured pre-dose and post-dose (see [Table 7-2](#), [Table 7-3](#), and [Table 7-4](#)). At all other visits, oxygen saturation will be measured pre-dose only.

If the patient receives supplemental oxygen, the amount [L/min] will be recorded in the eCRF.

Frequency: Visit 9 (Week 20), Visit 10 (Week 26), Visit 11 (Week 39), Visit 12 (Week 52), Visits 13 to 17 (Week 54 to 62), Visit 18 to Visit n (Open-label Extension Period), Termination Visit, and 30-day Safety Follow-up.

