8.4.3 Safety - amended

The incidence of treatment-emergent AEs (TEAEs) will be tabulated by treatment group. Adverse events are considered to be treatment-emergent if they have started or worsened after first application of study drug up to 2 days after end of treatment with study drug. Further tables will be produced for serious and/or drug-related treatment-emergent AEs, also treatment-emergent AEs leading to discontinuation of study drug and of special safety interest. The incidence of AEs during pre-treatment and during follow-up (ie, AEs occurring more than 2 days after end of treatment with study drug) will be tabulated separately. In addition to the summary tables of AEs, listings of SAEs, AEs leading to discontinuation of study drug and AEs of special safety interest will be provided.

Mortality in the study will be summarized descriptively. Any deaths in the study period will be listed, with day of death relative to start and stop of study drug and cause of death. Mortality is also defined as an exploratory efficacy parameter, and so being a binary outcome the difference in occurrence between treatment groups will be analyzed as described in Section 8.4.2.

The safety evaluation of laboratory data will include:

- Incidence rates of treatment-emergent laboratory values outside of normal range
- Incidence rates of pre-specified laboratory data abnormalities
- Descriptive analysis of continuous laboratory parameters and their changes from baseline by treatment group and visit.

Descriptive analysis of vital signs and their changes from baseline will be performed by treatment group and visit. Descriptive statistics of pulse oximetry and blood pressure/heart

rate measurements for the assessment of orthostatic changes will be performed by treatment group and visit.¹³³

For ECGs, the status pre-treatment and post treatment-initiation will be tabulated. The incidence rates of treatment-emergent ECG abnormalities will be tabulated by treatment group. A descriptive analysis of continuous ECG parameters and their changes from baseline by treatment group and visit will also be presented.

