13.4.1 Overview of changes to the study

This amendment was implemented based on the recommendation of the data monitoring committee (DMC) after review of the safety analysis on 01 MAR 2017. Due to increased complaints of both palpitations and dizziness in subjects with interstitial lung disease (ILD) noted by the DMC, the assessment of orthostatic changes in blood pressure and heart rate as well as the measurement of oxygen saturation (using forehead pulse oximetry) were added to the protocol assessments for all subjects. As recruitment for this study was already completed, the new assessments will not be implemented starting with the screening visit, but only for study visits, which will be performed after implementation of this amendment.

Additionally, an error in the description of the units provided in exclusion criterion 6 was corrected.

Correction of typographical errors and minor editorial changes are not specified in the list of changes below. New text is displayed as underlined; text that was deleted is presented as strike-through text.

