6.4.4 Subgroup analysis

A summary table (number and percentage of patients) of the following groups will be created by treatment group:

- Patients with ILD per MH (defined with PTs: interstitial lung disease and pulmonary fibrosis) by treatment group (already listed as subgroup analysis in [section 6.2.5](#))
- Patients with ILD confirmed by HRCT (confirmed, if interstitial fibrosis and /or ground glass found on HRCT) divided to sub-categories:
 - All patients with ILD per HRCT
 - All patients with ILD per HRCT done pre-therapy (HRCT prior randomization)
 - All patients with ILD per HRCT done post-baseline (HRCT after randomization)
- Patients with ILD per MH and confirmed by HRCT (if a patient with ILD in MH has HRCT done pre-randomization with interstitial fibrosis and/or ground glass found)
- Patients with worsening or new onset of ILD per AE (defined with PTs interstitial lung disease and pulmonary fibrosis in AE data)
- Patients with worsening or new onset of ILD (defined with PTs interstitial lung disease and pulmonary fibrosis in AE data) confirmed by HRCT (Worsening is confirmed, when interstitial fibrosis and/or ground glass finding is defined as worsened on HRCT. New onset is confirmed, when interstitial fibrosis and/or ground glass found on HCRT. HRCT confirms AE in question, if it has been done 28 days before – 28 days after AE start date and fulfills the requirements defined before.)

Descriptive analyses by ILD (yes/no) per MH will be performed as follows:

- TEAEs by treatment group
- TESAEs by treatment group
- Lung function tests (FVC%, FVC, DLco% predicted, DLco (mmol/min/kPa),) by treatment group
- Discontinuations of study medication by treatment group

Obligatory HRCTs were performed at baseline or during the study to be able to confirm possible ILD finding in MH or AE.

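### The extension SAP reports neither oximetry nor orthostatic results by ILD status, though an ILD signal prompted both, and it reduces the orthostatic data to a listing

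*SAP*

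**What the plan says.** The reason for the measurements is in Protocol 13.4.1 (Amendment 6): "Due to increased complaints of both palpitations and dizziness in subjects with interstitial lung disease (ILD) noted by the DMC". The new assessments "were added to the protocol assessments for all subjects", so patients with and without ILD both have them. They came late: "As recruitment for this study was already completed, the new assessments will not be implemented starting with the screening visit".

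Protocol 7.6.5 gives the orthostatic schedule as "Frequency: Visit 11 (Week 39), Visit 12 (Week 52), during the Dose-Titration Period of the Long-Term Extension Phase (Visits 13 to 17"). Protocol 7.6.18 starts oximetry at Visit 9. At visits with orthostatic testing, "oxygen saturation will be measured pre-dose and post-dose"; at other visits it is pre-dose only.

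On analysis, Protocol 8.4.3 commits to summarising pulse oximetry and says that statistics on blood pressure and heart "rate measurements for the assessment of orthostatic changes will be performed by treatment group and visit". It mentions no ILD split.

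The extension SAP, section 6.4.3, plans "Descriptive analysis of weight and vital signs, pulse oximetry and their changes from Week 52" and sends the orthostatic results to a listing. Section 6.4.4 then states "Descriptive analyses by ILD (yes/no) per MH will be performed as follows" and names four outputs: treatment-emergent adverse events (TEAEs), serious TEAEs, lung function tests (FVC and DLco) and discontinuations of study medication. Section 4.5.1 says that when a post-baseline visit holds several values, the latest available one is analysed, and that Week 52 is the extension baseline.

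**The concern.** The SAP takes ILD seriously. It defines ILD by medical history and by HRCT, and plans safety outputs by ILD status. Yet the two objective measures that were added because of an ILD observation are not among those outputs.

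The extension is where this matters most. Patients formerly on placebo take their first riociguat dose at Visit 12 and titrate through Visit 17 with both measures in place. In the main phase neither measure was scheduled at Visits 1-6, so the start of riociguat went unobserved on them. SAP 4.4 also plans no data monitoring committee for the extension, which makes the tabulated outputs the main planned route for following the signal.

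If saturation changes mainly in ILD patients, an undivided mean dilutes that change. For orthostatic change there is no summary at all, so a reader would have to build one from a listing.

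**Working it through.** No sample size, power or error-rate figure bears on this point. The check sets the sections side by side and counts.

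**1. By-ILD safety outputs (SAP 6.4.4)**

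| Output | SpO2 included? | Orthostatic BP/HR included? |
|---|---|---|
| TEAEs | No | No |
| Serious TEAEs | No | No |
| Lung function (FVC, DLco) | No | No |
| Discontinuations | No | No |

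Result: 0 of 4 for each measure. The only other use of ILD as an analysis subgroup is for change in mRSS (SAP 6.2.5).

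**2. Orthostatic data**

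- Protocol 8.4.3: descriptive statistics, by treatment group and visit.
- SAP 6.4.3: listing only, so 0 summary tables.
- SAP section 7, which is headed as covering changes in the planned analysis, records only two SAP approvals and does not mention this reduction.

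This is a mismatch between the documents and does not depend on ILD.

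**3. Pre-dose and post-dose SpO2**

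- Visits 12 to 17 are 6 visits. With a pre-dose and a post-dose reading at each, the schedule gives 6 × 2 = 12 readings for a patient measured at every one.
- The rule in SAP 4.5.1, read literally, keeps one reading per visit, the later one. That leaves 6 of the 12, all post-dose, and no within-visit change.
- Week 52 adds an ambiguity. Visit 12 is post-baseline for the main phase and baseline for the extension, and the SAP does not say which reading serves. In former placebo patients the pre-dose reading precedes their first riociguat dose and the post-dose reading follows it.

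**4. Dilution**

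If a fraction p of patients has ILD, the undivided mean change is p × (mean change with ILD) + (1 − p) × (mean change without ILD). The documents give neither p nor an expected change, so no figure can be attached.

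**5. Limits on the data themselves**

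- There are no pre-treatment values, because recruitment was complete when the measures were introduced.
- Week 52 is an on-drug baseline for patients randomised to riociguat who remained on it.
- Only visits after Amendment 6 took effect (approved 02 May 2017) carry the measures, so the number of former placebo patients with ILD and Visit 12-17 data is unknown.

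**The case against.** The strongest case against the point has five parts.

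- **The complaints are already covered.** What the DMC noted was palpitations and dizziness. Reported as adverse events, these fall in the by-ILD TEAE tables. This stands, and no extra symptom table is needed. The objective measures are a separate matter and are not covered.
- **No ILD split was promised.** Amendment 6 gives ILD as the trigger, and Protocol 8.4.3 asks for treatment group and visit only. The post-dose readings also serve individual titration decisions (Protocol 4.1.2). This stands too: a reader might infer that the SAP breaks a protocol commitment on ILD, and it does not. The missing split is an analysis gap. The documented mismatch is the reduction of orthostatic data to a listing.
- **Masking is limited.** No orthostatic mean is planned that could hide anything, and SAP 4.1 provides minimum, median and maximum as well as the mean. An extreme desaturation would therefore be visible, though not linked to ILD.
- **A programmer may separate pre-dose from post-dose anyway.** That is plausible, but the SAP does not say so.
- **The setting is exploratory.** The SAP calls its results exploratory and warns about group comparisons, and the study was being terminated. This limits the weight of the point, but continued benefit-risk assessment is the SAP's stated focus.

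A reader might also infer that the data cannot answer the DMC's question. The documents do not support that: the measures were taken in all subjects, ILD status is defined, and the orthostatic values are listed.

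**Conclusion.** The point holds for the extension SAP's planned outputs. None of its four by-ILD safety outputs includes oximetry or orthostatic change. The orthostatic data get no summary table although Protocol 8.4.3 specifies one. The rule on repeated values leaves pre-dose and post-dose SpO2 unseparated and, read literally, would drop the pre-dose reading at Visits 13-17, with Week 52 unclear.

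The conclusion rests on the text of the extension SAP alone. The main-phase SAP (version 4.0) and the benefit-risk SAP were not available, so nothing can be said about whether ILD splits were planned there. They would not remove the gap here, because this SAP presents itself as the full evaluation of the extension. The clinical size is unknown because no ILD count is given. Any table by ILD would be descriptive, with possibly small cells.

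**What to change.** **In SAP 6.4.3:**
- Summarise supine and sitting systolic pressure and heart rate, and the supine-to-sitting change, by treatment group and visit at Visits 12-17. Keep the listing.
- Exempt oximetry from the repeated-value rule in 4.5.1. Show pre-dose, post-dose and post-dose minus pre-dose SpO2 separately at Visits 12-17, and pre-dose only from Visit 18.
- State which Week 52 SpO2 reading is the extension baseline.

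**In SAP 6.4.4:**
- Add these SpO2 and orthostatic summaries to the by-ILD (yes/no) outputs, by treatment group. Label them exploratory and state the number of ILD patients with data at each visit.

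**In SAP section 7:** if the orthostatic data are to stay as a listing, record that as a change from Protocol 8.4.3 and give the reason.

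The cost is a few more descriptive tables from data already collected. The drawback is that some ILD cells may be too small to show more than individual values.

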7.1.2.5 Visit 12 (Week 52) - amended

This is the last visit of the main treatment phase, and the first visit of the long-term extension phase. At this visit, the patient should attend the clinic without having taken the morning dose of riociguat or placebo.

Before intake of study medication:

- Questionnaires (see Section 7.6.13)
- Smoking history
- Physical examination, including weight (Note: BMI will be calculated automatically in the eCRF)

- Oxygen saturation will be measured before and after intake of study drug (see Section 7.6.18, Table 7–2, Table 7–3, and Table 7–4).⁸⁰
- Vital signs (blood pressure and heart rate). Blood pressure and heart rate will be measured at all visits with the patient in a sitting position, after the patient has been at rest for at least 5 minutes. The same arm is always used for these measurements (see Section 7.6.5)
- Assessment of orthostatic changes: measure blood pressure and heart rate in supine position and sitting position approximately 2 h after intake of study drug (see Section 7.6.5).⁸¹
- mRSS (see Section 7.6.6)
- Digital ulcer net burden assessment (see Section 7.6.9)
- Patient’s and physician’s global assessment (see Section 7.6.15)
- Patient interference with skin assessment (see Section 7.6.16)
- Tender and swollen joint count assessment (see Section 7.6.14)
- Blood samples for safety (see Section 7.6.2)
- Pregnancy test (urine) for all women of childbearing potential (see Section 7.6.1)
- 12-lead ECG for centralized reading. A standard 12-lead ECG will be obtained with the patient in the supine position after resting for at least 5 minutes (see Section 7.6.7)
- Pulmonary function tests (FVC and DL_{CO}) (see Section 7.6.8)
- Recording and assessment of AEs (see Section 7.5)
- Concomitant therapy
- Drug accountability
- Start of long-term extension phase
- Assignment of patients to treatment with riociguat via IxRS, dispensation of study drug and intake by patient

After intake of study medication:

- Blood sample for PK (see Section 7.4)
 - PK blood sample between 1 – 2 hours after administration of the morning (first) dose of study medication
 - PK blood sample between 3 – 4 hours after administration of the morning (first) dose of study medication

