4.5.1 Definition of baseline and handling of repeated measurements

Baseline for the main phase is defined as the last set of non-missing measurements taken prior to the first intake of study medication, called ‘baseline for main treatment phase’.

In case of multiple measurements per post baseline visit, the last non-missing value per visit will be taken for analysis.

For LTE phase, Week 52 will serve as baseline measurement for LTE (‘baseline for LTE phase’) to be compared with measurements during the LTE phase.

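### Under the SAP's default rule, the extension-phase SpO2 change from Week 52 switches from post-dose to pre-dose readings at Visit 18, and the recorded oxygen flow is not used

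*SAP*

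**What the plan says.** SAP 6.4.3 covers oximetry in one sentence, shared with weight and vital signs: "Descriptive analysis of weight and vital signs, pulse oximetry and their changes from Week 52". It does not mention dose timing or oxygen.

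Two sentences in SAP 4.5.1 bear on which value is used. On repeats: "In case of multiple measurements per post baseline visit, the last non-missing value per visit will be taken for analysis". On the reference: "For LTE phase, Week 52 will serve as baseline measurement for LTE".

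The protocol sets what is collected:

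- **Visit 12 (Week 52), protocol 7.1.2.5:** "Oxygen saturation will be measured before and after intake of study drug". The dose taken at that visit is the first of the extension: "Assignment of patients to treatment with riociguat via IxRS, dispensation of study drug and intake by patient".
- **Visits 13 to 17, protocol 7.1.2.6 and Table 7-3:** again one reading before and one after the dose.
- **Visit 18 onward, protocol 7.6.18:** "At all other visits, oxygen saturation will be measured pre-dose only".
- **Oxygen, protocol 7.6.18:** "If the patient receives supplemental oxygen, the amount [L/min] will be recorded in the eCRF". No room-air reading is required.
- **Start of oximetry, protocol 13.4.1 (Amendment 6):** "the new assessments will not be implemented starting with the screening visit, but only for study visits" held after the amendment was implemented.

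**The concern.** A change from baseline is interpretable only if the two readings were taken under the same conditions. Two conditions can differ here.

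The first is timing relative to the dose. The rule that picks one value per visit yields a different kind of reading before and after Visit 18. That visit is also where blinded titration has ended and the open-label period begins, so a shift in the table at that point would invite a clinical explanation. In the Placebo-Riociguat group, a post-dose Week 52 reading would follow the patient's first riociguat dose and would not be an untreated baseline.

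The second is oxygen support. A patient who starts oxygen after a fall can show an unchanged SpO2, and a patient weaned after Week 52 can show a fall that is not real. The flow needed to tell these apart is collected, but the SAP gives it no role.

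At stake is whether one safety display can be read. Oximetry was added on a DMC recommendation about patients with interstitial lung disease (protocol 13.4.1), so the display will probably be looked at.

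**Working it through.** The plan states no SpO2 figure, so there is nothing to reproduce. The check sets the schedule beside the selection rule and then works out what follows.

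**Step 1. Which reading the rule selects**

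| Visit | Readings taken | Last non-missing value |
|---|---|---|
| 12 (Week 52) | pre-dose and post-dose | post-dose, if the rule is applied to the reference |
| 13 to 17 | pre-dose and post-dose | post-dose |
| 18 onward | pre-dose only | pre-dose |

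SAP 4.5.1 speaks of post-baseline visits. Week 52 is post-baseline for the main phase but is itself the baseline for the extension, so whether the rule reaches it is left open.

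**Step 2. Effect on the change score.** Let post-dose = pre-dose + delta, with no true change over time.

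- Post-dose Week 52 reference: change at Visits 13 to 17 = delta - delta = 0; change from Visit 18 = 0 - delta = -delta.
- Pre-dose Week 52 reference: change at Visits 13 to 17 = delta - 0 = delta; change from Visit 18 = 0 - 0 = 0.

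The step between Visit 17 and Visit 18 is -delta either way. The choice of reference only decides which side of the step carries the error. Assumed values of delta:

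| delta (points) | Step at Visit 18 |
|---|---|
| -2 | +2 |
| -1 | +1 |
| 0 | 0 |
| +1 | -1 |

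**Step 3. Oxygen, wholly by assumption.** If a share s of patients starts oxygen and it restores f points in each, the group mean hides s × f. With s from 2% to 10% and f from 4 to 6 points, this runs from 0.02 × 4 = 0.08 to 0.10 × 6 = 0.6 points.

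Errors in the two directions can also cancel. Take 50 patients. Three start oxygen after a true 8-point fall, half of it restored. Three others are weaned with no true change, where oxygen had raised the Week 52 reading by 4 points.

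- True mean change = -(3 × 8)/50 = -0.48.
- Recorded mean change = -(3 × 8 × 0.5 + 3 × 4)/50 = -(12 + 12)/50 = -0.48.

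The means agree, yet six patients are recorded at -4, when the truth is three at -8 and three at 0. A mean cannot show this; a count of patients whose oxygen changed can.

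**The case against.** The other side has a reasonable case.

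- **The plan does what the protocol asks.** Protocol 8.4.3 requires only descriptive statistics of oximetry by group and visit. SAP section 6 calls all extension results purely exploratory, and SAP 3.1 says the study was being terminated because development in this indication had stopped. This stands, and it limits the priority.
- **Unseen documents may settle it.** SAP 4.5 refers to Project Data Handling Rules and a dataset specification, SAP 4.1 to table standards, and section 1 to the main-phase SAP. None was supplied. This stands as a caveat, but the supplied text points the wrong way unless one of them overrides it.
- **Pre- and post-dose oximetry are separately scheduled procedures** (Tables 7-2 and 7-3), so they may not be the repeats that 4.5.1 has in mind and could be tabulated by timepoint. That is possible, and then no step would arise. The SAP does not say so.
- **Oxygen use may be rare.** Entry required FVC of at least 45% and DLco of at least 40% of predicted, and excluded pulmonary hypertension determined by right heart catheterization. This is fair, and it is why oxygen is the secondary point.
- **Worsening has other routes to detection:** adverse events, lung function and the interstitial lung disease tables in SAP 6.4.4. Also fair.

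A reader might infer that the SAP fixes no reading at all. It does supply a default, in 4.5.1; the trouble is that this default mixes readings.

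**Conclusion.** The point holds as a minor one. Applied as written, SAP 4.5.1 makes the SpO2 change from Week 52 a post-dose quantity at Visits 13 to 17 and a pre-dose quantity from Visit 18. The Week 52 reference is unnamed and, by the same rule, would be taken after the first extension dose. The resulting artefact at Visit 18 is exactly -delta. This assumes that one value per visit is kept, that both readings were obtained at Visits 13 to 17, and that no unseen document overrides the rule. The size of delta is unknown and may be zero.

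The secondary point also holds: the recorded oxygen flow has no role in the supplied SAP, so a stable SpO2 need not mean a stable patient. The figures for it are illustrations only.

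Two stronger inferences are not supported. A reader might conclude that desaturation is being hidden in this trial, but the documents give no SpO2 values and no oxygen use. A reader might also take oximetry to have been added because saturation fell; protocol 13.4.1 reports palpitations and dizziness in patients with interstitial lung disease, not desaturation. No test or decision rule depends on SpO2.

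**What to change.** Add to SAP 6.4.3:

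1. **Reading.** For the change from baseline, use the pre-dose SpO2 at Week 52 and at every extension visit, overriding 4.5.1. Summarise post-dose values and post-minus-pre differences at Visits 12 to 17 separately, so that the post-dose readings are not lost.
2. **Oxygen.** Show or flag readings taken on supplemental oxygen. Tabulate by treatment group the number of patients who start oxygen (none at Week 52, above 0 L/min later) or increase it (more L/min than at Week 52), and beside them those who stop or reduce it.
3. **No Week 52 reading.** Patients whose Week 52 visit came before Amendment 6 took effect have no reference and so no change score. Report them as a separate row of the oxygen count; do not drop them.

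Before programming, confirm that the eCRF distinguishes no oxygen from a missing entry, because the protocol asks for an amount only when oxygen is given.

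The cost is a few lines of SAP text, the separate post-dose summary and one small extra exploratory table whose counts may be zero. No measurement is needed beyond those the protocol already requires.
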